9.7.3 External data

The following data will be reported separately from CRFs:

- Laboratory test results.

9.8 Committees, meetings, etc.

9.8.1 Case review committee

Before the database lock, at a case review meeting, the sponsor, together with a medical expert, will check all data for all subjects recorded in CRFs. The subjects to be included in the analysis set will be decided upon on the basis of the outcome of the case review meeting and the definition of the analysis set in the protocol. Appropriateness of medical judgment of the principal investigator for the significant data affecting the safety or efficacy endpoint will also be evaluated during a case review meeting.

9.8.2 Safety monitoring committee

Depending upon the sponsor's requirements, reported interim safety data will be evaluated, and the sponsor will be notified as to whether the study should be continued, modified or discontinued. The evaluation will be performed in accordance with the Safety Monitoring Committee's standard operating procedures, which are set separately.

9.9 Study discontinuation or suspension

9.9.1 Discontinuation or suspension of entire study

The sponsor may discontinue or suspend the study when one or more of the following conditions is

applicable:

- Ensuring the safety of the study is difficult, for reasons such as multiple occurrence of serious adverse drug reactions.
- It is not considered possible to achieve the study objectives, for reasons such as not being able to enroll a sufficient number of subjects.

When discontinuing or suspending the study, the sponsor must report promptly to the principal investigator. The principal investigator or sub-investigator must promptly explain about study discontinuation or suspension to the participating subjects, and transfer them to other appropriate treatment.

Discontinuation criteria for each subject are shown in Section 4.5 .

9.9.2 Discontinuation or suspension of study at each study site

When ensuring the safety of the study is difficult, for reasons such as multiple occurrence of serious adverse drug reactions, the principal investigator may discontinue or suspend the study at the relevant study site after obtaining approval by the sponsor. If a major deviation from the protocol (including other procedures) and/or the GCP occurs, and is not resolved, the sponsor may request the principal investigator to discontinue or suspend the study at the relevant study site.

If the study is discontinued or suspended, the principal investigator or sub-investigator must promptly explain about the discontinuation or suspension to the participating subjects and the IRB, and transfer the subjects to other appropriate treatment.

9.10 Modifications to and deviations from the protocol

The principal investigator will perform the study in accordance with the study protocol approved by the IRB and regulatory authority, and provided by the sponsor. Protocol amendments require agreement by the principal investigator and sponsor. For any protocol amendment, written approval must be obtained from the IRB beforehand, unless such amendments are medically essential for avoiding immediate risk to the subject.

The principal investigator or sub-investigator must record deviations from the protocol and the reasons for these. In the event of an amendment to or deviation from the protocol in order to avoid immediate risk to the subject, the principal investigator must immediately submit a record of the deviation or amendment to the sponsor, study site, and IRB, and promptly obtain approval by the IRB. After obtaining approval by the IRB, the principal investigator will obtain written agreement by the sponsor, via the study site.

If deviation from the protocol is required as an emergency, in a medically unavoidable situation, such as in order to avoid immediate risk to the subject, the principal investigator will contact the sponsor in advance wherever possible to discuss how this should be handled. All deviations from the protocol should be recorded in the source documents.

9.11 Data management

The sponsor will commission data management tasks to a contract data management organization. Details of data management tasks will be defined in a separately specified procedures.

9.12 Storage of records

Study-related documents must be stored in accordance with the GCP and regulatory requirements. The principal investigator and study site must take measures to prevent accidental or premature disposal of the documents. When manufacture and marketing of the study drug has been approved, the sponsor will promptly report this in writing to the director of the study site.

The duration of storage of records will be until the later of the following:

- Three years after the date of achieving study drug marketing approval or after the decision to discontinue study drug development.
- Three years after study discontinuation or completion.

The above period of storage can be extended if necessary, as agreed upon with the sponsor. If the principal investigator cannot be responsible for storage of study-related records, this responsibility will be transferred to an appropriate successor.

9.13 Study quality control and quality assurance

The sponsor will define the procedures for quality control and quality assurance in the standard operation procedures in order to ensure that the study is performed, and that data, documents and reports are prepared in accordance with the protocol, GCP, and appropriate regulatory requirements. This study will be performed in accordance with ethical principles based on the Declaration of Helsinki, GCP, and other appropriate regulatory requirements.

The sponsor will hold explanatory meetings with the principal investigator and each study site before study initiation, and will provide education and training as required for study performance.

Appendix 1: Study Schedule

Visit	Screening period	Treatment period									Tapering period	Follow-up period
	1	2	3	4	5	6 ^b	7	8	disc ontin uation	9/dis conti nuati on	10	
Evaluation week	-3 to -1	0	1	2	3	4	5	6	-	7	8	
Obtaining informed consent or assent	X											
Demographic factors	X											
MINI-KID	X											
Inclusion/exclusion criteria:	X	X										
Physical Examination	X	X	X	X	X	(X)	X	X	X	X	X ^f	
Registration	X Pre- registration 1	X Registrati on										
CDRS-R	X	X	X	X	X		X	X	X			
CGI-S	X	X	X	X	X	(X)	X	X	X			
Psycho-education	X ^c	X ^c			X ^c			X ^c	X ^c			
C-SSRS	X	X	X	X	X	(X)	X	X	X	X		
Study drug administered		X	X	X	X	(X)	X	X ^d	X ^d			
Adherence of drug administration			X	X	X	(X)	X	X	X	X		
Randomization		X										
Laboratory tests ^a	X				X			X	X	X		
Blood pressure, pulse rate	X	X	X	X	X	(X)	X	X	X	X		
ECG	X							X	X	X		
Body weight		X						X	X	X		
Urinary drug screening		X										
Pregnancy test (post-menarche females only)	X								X ^e	X		
Adverse events	X											

a Hematology tests, blood chemistry tests, and urinalysis. HbA1c, TSH, FT3 and FT4 measurements are only performed at Visit 1.

b Visit 6 is a visit that can be made to the hospital in connection with dose increase, decrease, etc. If Visit 6 is made, observations and tests are performed as far as possible.

c Psycho-education is provided after evaluation of CDRS-R and CGI-S.

d Tapering-period prescription.

e Performed at discontinuation if not performed during the tapering period.

f Adverse events up to 7 days after the final administration of the study drug will be investigated. The subject is checked by telephone or other appropriate method, even if he/she fails to make a visit.

Appendix 2: Management of abnormal hepatic function test results, and discontinuation criteria

In order to ensure subjects' safety, as well as to evaluate the causes of any hepatic dysfunction found, management on the basis of abnormal hepatic function test results, and the discontinuation criteria, are defined, on the basis of the FDA's July 2009 guidance (Guidance for Industry Drug-Induced Liver Injury: Premarketing Clinical Evaluation).

(1) Hepatic dysfunction criteria

The principal investigator or sub-investigator confirms whether or not the subject's laboratory test results meet any of the following criteria:

- a. AST and/or ALT >5 times the upper limit of normal (ULN) .
- b. AST and/or ALT >3 times the upper limit of normal (ULN) , and total bilirubin >2 times the upper limit of normal (ULN) .
- c. AST and/or ALT >3 times the upper limit of normal (ULN) , and signs and/or symptoms consistent with hepatitis or hypersensitivity (e.g. fatigue, nausea, vomiting, right upper abdominal pain or tenderness, jaundice, fever, rash, eosinophil increase by more than 5%).

(2) Principal investigator's actions

If one or more of the above hepatic dysfunction criteria is met, the principal investigator or sub-investigator will act as follows:

- Immediately ensure that the subject stops taking the study drug.
- If possible, have the subject visit hospital within 72 hours after the abnormalities are first found, to repeat the hepatic function tests for a supplementary evaluation of hepatic function.
- Until the hepatic function test result (ALT, AST, ALP, and total bilirubin) abnormalities cease, stabilize, or return to within the reference range or to the baseline, the subject's progression is observed two to three times per week, if possible.
- Report to the sponsor using the hepatic dysfunction follow-up assessment form, within 72 hours after the relevant abnormalities coming to the principal investigator's attention.
- Look into the option of consulting a hepatologist or other specialist.
- Look into the option of performing hepatic imaging, such as ultrasonography, magnetic resonance imaging, or computed tomography.
- Report all events that meet criterion b (above) as serious adverse events.

(3) Follow-up assessment

If one or more of the above hepatic dysfunction criteria is met, items including the following will be assessed at the time of the follow-up assessment visit, and the results will be entered in the hepatic dysfunction follow-up assessment form:

- Clinical symptom.

- Alcohol intake.
- Risk factors for nonalcoholic steatohepatitis (NASH) (e.g. diabetes, obesity, and hypertriglyceridemia).
- Autoimmune hepatitis and cholangitis.
- Wilson's disease.
- Laboratory tests:
 - The following serum tests relating to viral hepatitis:
 - > Hepatitis A IgM antibody
 - > Hepatitis B surface antigen and hepatitis B core antibody
 - > Hepatitis C RNA
 - > Hepatitis E IgA antibody
 - > Cytomegalovirus IgM antibody
 - > Epstein-Barr virus capsid antigen IgM antibody
 - In the case of subjects with total bilirubin >1.5 times the upper limit of the reference values, conjugated bilirubin will be measured.
 - Blood cell measurement will be carried out, including leukocyte fractions.

MedDRA	Medical Dictionary for Regulatory Activities
MINI-KID	Mini International Neuropsychiatric Interview for children and adolescents
MMRM	mixed-effects model repeated measures
PPS	Per Protocol Set
SMQ	Standard MedDRA Queries

# 1. Introduction

This document presents in concrete terms the contents of Section 8 (Statistical analysis) of the study protocol (study no.: 1701A3631). This document will be fixed before the key break. With respect to the details of the output from the analysis results stated in the statistical analysis plan, the analysis figures and tables output plan (mock tables, listings and figures) will be prepared separately.

# 2. Study summary

This study is a multicenter, randomized, placebo-controlled, double-blind, parallel-group, comparative study with children’s and adolescent patients with depressive disorder, with the target number of subjects being 148. It consists of the following four periods: Screening period (1-3 weeks), treatment period (6 weeks), Tapering period (1 week), Follow-up period (1 week), (total: up to 11 weeks). Subjects whose eligibility has been confirmed after obtaining informed consent will be pre-registered (Visit 1), and, after completion of the 1- to 3-week screening period, their eligibility will be confirmed again, and they will be registered (Visit 2). Registered patients will be allocated randomly to either the duloxetine group or placebo group, in a 1:1 ratio, and will be orally administered duloxetine or placebo once daily after breakfast, under double-blind conditions. With the duloxetine group, administration will be initiated at 20 mg/day, and increased to 40 mg/day at Visit 3, 1 week later. From Visit 4, 1 week after Visit 3, the dose can be increased or decreased between 40 and 60 mg/day, in accordance with stipulations in the study protocol. Subjects who are to transfer to the extended long-term treatment study (study no.: 1702A3632) will do so after completion of the tapering period.

# 3. Study objectives

## 3.1 Primary objective

To verify the superiority of duloxetine over placebo, using as the index change from baseline in total

children's depression rating scale - revised (CDRS-R) score.

### 3.2 Secondary objectives

- To evaluate the efficacy of duloxetine compared with placebo on the basis of the following indices:
  - 30% response rate: Proportion of subjects showing CDRS-R total total score decreases of 30% or more from baseline.
  - 50% response rate: Proportion of subjects showing CDRS-R total total score decreases of 50% or more from baseline.
  - Remission rate: Proportion of subjects with CDRS-R total scores of 28 or lower
  - Change from baseline in CDRS-R subscales and item 13 (suicidal ideation)
  - Change from baseline in clinical global impression: severity (CGI-S) score
  
- To evaluate the safety of duloxetine, with occurrence or non-occurrence and frequency of adverse events and adverse drug reactions as indices.

## 4. Study design

### 4.1 Observation schedule

A schedule table is presented in Appendix 1.

### 4.2 Allocation method

The subjects whose eligibility is confirmed after completion of the screening period will be allocated to either the duloxetine or placebo group in a ratio of 1:1, by the stochastic minimization method, using age (<12, ≥12) and study site as allocation factors.

Consideration should be given so that the maximum inter-group difference at each study site does not exceed two subjects.

### 4.3 Target number of subjects

The target number of subjects will be 148 (74 each in the duloxetine and placebo groups).

Rationale for the target sample size:

The number of subjects has been set with reference to the results obtained in two overseas, Phase-3 studies, the HMCL and HMCK studies, with the target population planned for the present study, that is, patients who were aged ≥9 when informed consent was obtained, and ≥7 at initial onset of depressive symptoms. In addition, the number of subjects in the present study has been set with the expectation that more accurate selection of institutions and subjects will enable minimization of the placebo response, and thus increase in the inter-group difference.

In this study, the inter-group difference (placebo - duloxetine) between the duloxetine group and the placebo group in CDRS-R change to week 6 of the treatment period is assumed to be 5.9, the standard deviation in CDRS-R change is assumed to be 12.0 in both groups, and the effect size is predicted to be

0.49. It is thus estimated that 66 subjects per group (total: 132) will be required to achieve a detection power of 80% or higher in a two-sample t-test at a two-sided significance level of 0.05. Therefore, predicting the dropout rate to be 10%, the target total number of subjects has been set at 148 (74 per group).

## 5. Analysis sets

As efficacy analysis sets, a full-analysis set (FAS) and a per-protocol set (PPS) will be established as defined below. The FAS will be the primary analysis set, whereas the PPS will be used for sensitivity analysis in the primary analysis of the primary endpoint. In addition, for analysis of safety, a safety-analysis set will be established.

### 5.1 FAS

This comprises all randomized subjects to whom the study drug has been administered at least once, and with whom the CDRS-R total score has been determined at baseline and at least once after initiation of study drug administration. Even in the event of an incorrect prescription during the study, analysis of the FAS will be performed with the allocated group.

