8.3 Analysis sets

The following analysis sets are defined:

Full-analysis set (FAS)

This comprises all randomized subjects to whom the study drug has been administered at least once, and with whom the CDRS-R total score has been determined at baseline and at least once after initiation of study drug administration. Even in the event of an incorrect prescription during the study, analysis of the FAS will be performed with the allocated group.

Safety-analysis set

This comprises all randomized subjects to whom the study drug is administered at least once. Analysis of this set will be performed with subjects actually administered the study drug, rather than allocated group.

Per-protocol set (PPS)

This comprises all randomized subjects who are included in the FAS, and to whom neither of the following conditions apply:

- Not meeting the inclusion criteria, and/or violating the exclusion criteria, in the protocol
- Insufficient compliance in study drug use.
- Violation of restrictions on concomitant treatment.

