### 6.4 Handling of missing data

In principle, missing data will not be imputed. If missing data for CDRS-R total scores 6 weeks after initial administration are nevertheless imputed for the secondary efficacy analyses, this will be performed by the last observation carried forward (LOCF) method, baseline observation carried forward (BOCF) method, and modified BOCF method.

If missing data imputation is performed by the LOCF method, the measurements used as substitutes will be those obtained at the latest scheduled evaluation time-points (Visits 3, 4, 5, 6 and 7) before the missing-data time-points.

If missing data imputation is performed by the BOCF method, the baseline data will be used as substitutes.

The modified BOCF method is defined as follows:

- With subjects withdrawn from the study due to adverse events and/or insufficient efficacy, imputation will be by the BOCF method.
- With subjects withdrawn from the study for any reason other than the above, imputation will be by the LOCF method.

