### 9.2.1 Analysis of secondary efficacy endpoints

#### 1) Analysis of response rate and remission rate

For each of the indices defined below, the number of responders (number of subjects showing remission) and response rate (remission rate) will be obtained for each treatment group, at weeks 1 to 3, 5, and 6 of administration, and at the final evaluation (week 6 of administration, or at discontinuation of the treatment period), and the Cochran-Mantel-Haenszel test, with stratification by the allocation factor age (<12, ≥12), will be used to compare the duloxetine and placebo groups. In addition, the inter-group difference in response rate (remission rate), and the 95% confidence interval, will be calculated.

Index	Definition
30% response	Reduction of 30% or more in CDRS-R total score compared with baseline
50% response	Reduction of 50% or more in CDRS-R total score compared with baseline
Remission	CDRS-R total score of 28 or less

An analysis with withdrawn subjects taken to be non-responders (non-remission subjects) will also be performed.

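### Treated subjects with no CDRS-R after dosing fall outside the FAS, so the supportive BOCF, modified BOCF and withdrawn-as-non-responder analyses omit some very early withdrawals that their own rules could score

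*SAP*

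**What the plan says.** SAP 5.1 defines the FAS as randomised subjects who took study drug and whose "CDRS-R total score has been determined at baseline and at least once after initiation of study drug administration". Protocol 8.3 carries the same condition: "at least once after initiation of study drug administration". SAP 9 and its Table 1 analyse every efficacy endpoint in the FAS and add the PPS only for the primary analysis. The one set without a post-dose rating requirement is the safety-analysis set (SAP 5.3), which is not used for efficacy.

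The rules for the supportive analyses are:

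- **BOCF** (SAP 6.4, 9.1.2): a missing week-6 score is replaced by the baseline score.
- **Modified BOCF** (SAP 6.4): "With subjects withdrawn from the study due to adverse events and/or insufficient efficacy, imputation will be by the BOCF method". Withdrawals for other reasons get LOCF.
- **Response and remission** (SAP 9.2.1): "An analysis with withdrawn subjects taken to be non-responders (non-remission subjects) will also be performed".
- **Tipping point** (SAP 9.1.2, item 3): multiple imputation, then a shift applied to imputed values in the duloxetine arm only.

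The first scheduled CDRS-R after dosing is Visit 3, day 7 ± 3 (Protocol Table 7-3). Protocol 7.5.1 also asks for a rating at discontinuation, but only where it can be obtained. No CDRS-R is scheduled after the treatment period (Protocol Appendix 1).

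**The concern.** FAS membership depends on something that happens after randomisation. For an MMRM this costs almost nothing, because a subject with no post-baseline value adds nothing to the likelihood. BOCF and non-responder counting are different: each can score a subject from the baseline value or from the fact of withdrawal. The same holds under modified BOCF for withdrawals due to adverse events or insufficient efficacy. The set therefore removes subjects that the methods were able to keep.

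Those removed would count as no improvement or non-response. Leaving them out raises the apparent improvement in their arm. If the arms lose different numbers, the treatment difference in these analyses shifts for a reason unrelated to the drug's effect in the subjects who were rated.

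**Working it through.** **1. The plan's own figure.** SAP 4.3 states that the difference in "CDRS-R change to week 6 of the treatment period is assumed to be 5.9" and that the "standard deviation in CDRS-R change is assumed to be 12.0 in both groups", and asks for "power of 80% or higher in a two-sample t-test". A noncentral-t calculation (difference 5.9, SD 12.0, two-sided 0.05) gives 66 per group, with power 80.05%. Allowing for 10% dropout, 66/0.90 = 73.3, so 74 per group and 148 in total. The plan reproduces, and 10% of 148 is 14.8, or about 15 dropouts.

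**2. Assumptions not in the documents.**

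- Mean change in duloxetine completers is -20 (range -15 to -25). The placebo change is 5.9 less.
- The 15 dropouts split 8 on duloxetine and 7 on placebo.
- Of these, e per arm have no CDRS-R after dosing.
- Covariate adjustment is ignored.

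**3. BOCF formula.** With dropouts scored 0, an arm's mean improvement is (completers × mean improvement)/(74 - e), where e = 0 if everyone is kept.

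**4. BOCF results at -20 (placebo -14.1).**

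- All kept: 66×20/74 - 67×14.1/74 = 17.84 - 12.77 = 5.07.
- Omit 2+2: 66×20/72 - 67×14.1/72 = 18.33 - 13.12 = 5.21.
- Omit 2 on duloxetine, 0 on placebo: 18.33 - 12.77 = 5.57.
- Omit 4 on duloxetine, 0 on placebo: 66×20/70 - 12.77 = 18.86 - 12.77 = 6.09.
- Omit 0 on duloxetine, 2 on placebo: 17.84 - 13.12 = 4.72, a move in the opposite direction.

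| Omitted (duloxetine + placebo) | -15 | -20 | -25 | Shift |
|---|---|---|---|---|
| none | 5.14 | 5.07 | 5.00 | – |
| 2+2 | 5.28 | 5.21 | 5.14 | about 0.1 |
| 2+0 | 5.51 | 5.57 | 5.62 | 0.4 to 0.6 |
| 4+0 | 5.90 | 6.09 | 6.28 | 0.8 to 1.3 |

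**5. Withdrawn as non-responders.** Assume 50% response in 55% of duloxetine and 40% of placebo completers. The difference with all kept is 66×0.55/74 - 67×0.40/74 = 12.8 percentage points. It becomes 14.2 at 2+0 and 15.6 at 4+0. With 45% and 30% the figures are 13.0, 14.1 and 15.3. The shifts run from about 1 to 3 points.

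**6. Tipping point.** The penalty left out is (e/74) × k × 5.9, or 5.9/74 = 0.08 points per omitted duloxetine subject at k = 1.

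**7. A deliberately adverse case.** Take dropouts as 10 on duloxetine and 5 on placebo, with 4+0 omitted. At -20, the BOCF difference goes from 64×20/74 - 69×14.1/74 = 4.15 to 64×20/70 - 69×14.1/74 = 5.14. Treating expected values as if observed, p goes from 0.047 to 0.015. Over the range -15 to -25, p is 0.025 to 0.084 with all kept and 0.010 to 0.021 with the four omitted.

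**The case against.** Several points on the other side stand.

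- **No formal decision rests on these analyses.** Change in CDRS-R total score is the only primary endpoint. Protocol 8.10.3 describes the BOCF and modified BOCF analyses as exploratory. Neither document says they are there to penalise dropouts, so that purpose should not be attributed to the plan.
- **Not every early dropout is lost.** A child who stops on day 2 and is rated at discontinuation meets the FAS wording. Only treated subjects with no later CDRS-R at all are excluded, probably a small part of the 15 or so expected dropouts. SAP 6.3 does leave unclear how a discontinuation rating before day 4 is used, since it fits no post-dose visit window.
- **The loss will be visible.** SAP 7.1.1 already reports FAS exclusions by group with reasons. That discloses an imbalance but does not correct the estimates.

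A reader might infer that the omission favours duloxetine. The documents give no figure for early withdrawal by arm, and an excess on placebo would shrink or reverse the shift. A reader might also infer that it could decide whether BOCF reaches significance. In the adverse case above, p crosses 0.05 only towards the -25 end of an assumed range. Nor is the tipping-point analysis materially compromised: 0.08 points per subject is negligible.

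**Conclusion.** The exclusion is real and follows from the FAS definition together with SAP 9. It affects three supportive analyses and leaves the primary MMRM essentially untouched. Under the stated assumptions the BOCF difference moves by about 0.1 points for a balanced loss of two per arm and by 0.4 to 1.3 points for a loss of two to four on duloxetine only. For scale, the planned standard error of the difference is 12×√(2/74) = 1.97. The size and direction depend on counts that the documents do not contain, so this is a possible distortion and not a demonstrated bias. It is worth correcting because the correction needs no new data and removes a post-randomisation exclusion that these methods do not require.

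**What to change.** Before key break, define a second efficacy set in the SAP: all randomised subjects who took at least one dose and have a baseline CDRS-R, analysed by allocated group. Use it for the BOCF, modified BOCF and withdrawn-as-non-responder analyses. Score subjects with no later value as no change (BOCF, modified BOCF) or as non-response and non-remission. State that, under modified BOCF, this includes subjects who withdrew for other reasons, because LOCF has nothing to carry forward for them. Keep the FAS for the MMRM.

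Adding these subjects to the tipping-point analysis is optional. If it is done, impute them from baseline and covariates. Setting them to no change would not fit a multiple-imputation method.

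The cost is one more set to define, matching edits to SAP 6.4, 9.1.2, 9.2.1 and Table 1, and a stated reason in the SAP for departing from Protocol 8.3, as Protocol 8.1 requires. The sample size does not change.
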